## Revision History

## **1 PROTOCOL SUMMARY**

### **Efficacy and Safety of EndoBar Bariatric Embolization for Weight Management in People with Obesity**

#### **Study Objective**

To evaluate the efficacy and safety of the Endobar gastric embolization system for the treatment of obesity before continuing to a larger Pivotal Trial.

#### **Investigational Device**

The investigational device in this clinical study is the Endobar Infusion Catheter System – a disposable system consisting of an occlusion balloon catheter, a Smart Manifold delivery system.

#### **Study Design/Planned Number of Subjects**

This study is a prospective, sham controlled, single-blind 12-month trial with 1:1 randomization. A maximum of 40 subjects (obese men and women who have a body mass index (BMI) of 35.0–55.0 kg/m^2) will be enrolled in the study. Eligible subjects will be randomized to treatment with Endobar Therapy (n = 20) or sham procedure control (n = 20). Endobar Therapy involves catheter-based embolization of the left gastric artery. All subjects in both Endobar Therapy and Sham Control groups will receive Lifestyle Therapy (behavioral and diet education). At the end of 6 months all subjects randomized to the Sham Control group will receive catheter-based embolization of the left gastric artery. Both Endobar Therapy and Sham Control crossover to Endobar Therapy groups will be followed for a total of 12 months.

#### **Study Duration**

The duration of the study is expected to last approximately 18 months from the first enrollment. An additional 12 months to the study closeout after the last follow-up.

#### **Sample Size**

This study is powered to detect a differential change in total body weight loss between groups. Briefly, 18 patients are required in each group to have an 85% chance of detecting, as significant at an alpha of 5%, a change in total body weight loss of 5% in the Control group to 10% in the GAE group (assuming a standard deviation of 5%), and 1:1 randomization. Again, assuming a 10% loss to follow-up, a total of 20 patients are required per group. Secondary endpoints will be evaluated using descriptive statistics.

### **Primary Endpoints**

Percent total body weight loss at 6 months and at 12 months are the primary endpoints intended to provide efficacy and safety of investigational device.

- Efficacy Endpoints: The primary efficacy endpoints of the study will be difference in percent total body weight loss at 6 months between Sham Control and Endobar Therapy groups and percent total body weight loss at 12 months in the group randomized to initial Endobar Therapy. Success will be defined as: 1)  $\geq 5\%$  total body weight loss at 6 months with statistical superiority to the Sham Control group and 2)  $\geq 5\%$  total body weight loss at 12 months.
- Safety Endpoints: All participants will be carefully monitored by a physician and research nurse during this study. Safety will be monitored by:
  - Incidence of device-, procedure- and therapy- related adverse events
  - Incidence of device related, or unrelated, serious adverse events, including unanticipated adverse device effects

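### Non-serious harm counts only when judged related, so its between-arm comparison depends on attribution and has no all-cause sham rate beside it

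*Combined protocol and SAP*

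**What the plan says.** The Protocol Summary, under Primary Endpoints, lists two safety measures:

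- "Incidence of device-, procedure- and therapy- related adverse events"
- "Incidence of device related, or unrelated, serious adverse events, including unanticipated adverse device effects"

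The second covers serious events whether or not they are related to the device. The first is the only line through which a non-serious event can enter, and it requires a judged link to the device, the procedure or the therapy. The same section adds: "All participants will be carefully monitored by a physician and research nurse during this study".

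Study Design/Planned Number of Subjects describes a "prospective, sham controlled, single-blind 12-month trial with 1:1 randomization", with 20 subjects per arm and Lifestyle Therapy in both. The controlled period is limited: "At the end of 6 months all subjects randomized to the Sham Control group will receive catheter-based embolization of the left gastric artery".

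The text reviewed does not say who judges relatedness, whether that person knows the allocation, by what rule the judgement is made, or how safety is to be compared between arms. It does not say whether therapy in the first measure means Endobar Therapy, Lifestyle Therapy or both.

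**The concern.** A concurrent sham arm shows how often symptoms such as nausea or abdominal pain occur without embolization, from the procedure itself, the change of diet or background illness. An all-cause count by arm uses that information directly. A related-only count passes each event through a causality judgement first.

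That judgement is unlikely to work the same way in both arms. Before crossover a sham subject has had no embolization, so an event cannot properly be put down to it. The same symptom in an Endobar subject can be. Single-blind does not say which party is blinded, and nothing in the text reviewed keeps allocation from the person judging cause. If attribution differs by arm, the related-only difference mixes the effect of treatment with the difference in attribution. The listed endpoints include no all-cause figure against which to check it.

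What is at stake is one of the two aims under Study Objective: safety before a larger pivotal trial. Key Exclusion Criteria shows that gastric harm is a recognised issue, since it excludes ulcer history, ulcer-causing medication, and significant mucosal inflammation, ulceration or ischemia on endoscopy. Milder gastrointestinal events may never be classed as serious, and would then appear only in the filtered measure.

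**Working it through.** **Inputs.** Arm sizes of 20 and 20, the 6-month controlled period and the two safety measures come from the Protocol Summary. It gives no adverse event rates, so every rate below is an assumption chosen to show the mechanism.

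**The plan's own figure.** The only stated calculation is for efficacy: n = 2 × (1.960 + 1.036)² × (5/5)² = 17.96, so 18 per group, and 18/0.90 = 20 after 10% loss. It reproduces with a two-sided 5% test and 85% power. It fixes the arm size but neither supports nor weakens this point.

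**All-cause difference.** Assume gastrointestinal symptoms by month 6 in 6/20 sham subjects (30%) and 10/20 Endobar subjects (50%).

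- Difference: 50 − 30 = 20 points.
- Standard error: √(0.50 × 0.50/20 + 0.30 × 0.70/20) = √0.0230 = 0.152.
- Half-width: 1.96 × 0.152 = 0.297, about 30 points.
- Approximate 95% CI: −10 to +50 points.

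**Related-only difference.** Let a1 and a0 be the fractions of affected Endobar and sham subjects whose event is judged related. The difference is 50a1 − 30a0 points.

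| a1 | a0 | Endobar, % | Sham, % | Difference, points |
|---|---|---|---|---|
| 1 | 1 | 50 | 30 | 20 |
| 0.5 | 0.5 | 25 | 15 | 10 |
| 0.5 | 0.25 | 25 | 7.5 | 17.5 |
| 0.5 | 0 | 25 | 0 | 25 |
| 0.3 | 0.5 | 15 | 15 | 0 |

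With equal attribution (a1 = a0 = a) the result is 20a: the direction is kept and the size is scaled by a. With unequal attribution the same underlying events can give a larger difference or none.

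**No true harm.** Assume the same background rate b in both arms and no device effect, so the all-cause difference is 0. With half the background events called related in the Endobar arm, the related-only difference is b × (0.5 − a0):

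| b | a0 = 0 | a0 = 0.25 | a0 = 0.5 |
|---|---|---|---|
| 20% | +10 | +5 | 0 |
| 40% | +20 | +10 | 0 |

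Unequal attribution creates an excess of 5 to 20 points where there is none. Equal attribution creates no distortion here.

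**The case against.** A reader might infer that the sham arm cannot supply any comparison, that its related rate is zero by construction, and that the apparent excess could therefore lie anywhere from 0 to 50 points under the rates above. The documents do not support that. The first measure includes procedure-related events, and sham subjects have a sham procedure. Follow-up Schedule also lists an interventional radiology procedure before randomization, which suggests that both arms share one. If therapy includes Lifestyle Therapy, further sham events can qualify. A zero sham rate follows only if procedure is dropped from the measure and therapy is read as Endobar Therapy alone.

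A second tempting inference is that unrelated non-serious events will go unrecorded. The plan defines what is reported as an endpoint, not what is collected, and it has all participants monitored. If every event is recorded, an all-cause table can be made without any change to the endpoint. The text reviewed is a protocol summary, so collection and adjudication rules may stand elsewhere, and their absence here is weak evidence that they do not exist.

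Three further points stand. Serious events are already counted regardless of cause, so that comparison is untouched. No safety hypothesis, threshold or go/no-go rule in the text depends on the non-serious rate. All-cause counting is not a full cure either: if staff or subjects know the allocation, the eliciting and reporting of symptoms may still differ by arm.

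None of this removes the core of the point. The listed non-serious measure depends on attribution, equal attribution is not assured by anything in the text, and no all-cause non-serious rate is among the endpoints.

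**Conclusion.** The point holds as a risk of bias and a gap in reporting. As listed, the comparison of non-serious harm depends on relatedness judgements that may differ by arm, and it comes without an all-cause sham background rate.

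The size is not known, because the documents give no event rates and no attribution rule. Under the assumed rates, the related-only difference can depart from the 20-point all-cause difference in either direction, and a spurious excess of 5 to 20 points can arise with no true harm. These figures rest on the assumed rates and on attribution that differs by arm. With equal attribution the bias between arms disappears, although the difference is still scaled down.

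The conclusion is limited to non-serious events before crossover and to the text reviewed. This is a cheap improvement rather than a defect that invalidates the safety assessment.

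**What to change.** Keep the related-event measure and add to the safety endpoints: the incidence of all adverse events, serious and non-serious, regardless of attribution, recorded in both arms and tabulated by randomized arm from the index procedure up to but not including the month-6 crossover. Report the Endobar-minus-sham risk difference with an exact 95% CI, overall and for gastrointestinal events, and present it as descriptive given 20 per arm. State what therapy covers in the related-event measure, who judges relatedness, and whether that person is blinded.

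The cost is one line of endpoint wording and one table. Non-serious events judged unrelated must be recorded and coded in both arms, if that is not already planned. Reported rates will look higher than related-only rates. The intervals will be wide, with a half-width of about 30 points under the rates assumed above. No additional subjects are needed. The wording should be settled before enrolment, because events that were never recorded cannot be recovered.

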### **Secondary Endpoints**

The secondary outcomes measured at 6 and 12-months are:

- Percent excess weight (%EWL), defined as absolute weight loss divided by baseline excess weight and multiplied by 100, at 6 months and at 12 months. Excess weight will be determined from ideal body weights based on a  $BMI=25\text{ kg/m}^2$
- Proportion of subjects who achieve  $\geq 5\%$  and  $\geq 10\%$  total body weight loss from baseline at 6 months and at 12 months.
- Percent change in selected coronary heart disease risk factors (plasma triglyceride and HDL-cholesterol, and systolic and diastolic blood pressure) at 6 months and at 12 months
- Success of performing the radiological procedure

### **Additional Endpoints of Interest (assessed at baseline and at 6 and 12 months)**

- Changes in mood (depression/anxiety)
- Change in quality-of-life
- Change in eating behavior
- Change in volume of Ensure consumed to achieve satiation
- Change in plasma ghrelin and glucagon-like peptide 1 concentrations
- Change in oral glucose tolerance and insulin sensitivity

### **Key Inclusion Criteria**

- $BMI\ 35.0\text{--}50.0\text{ kg/m}^2$  at time of screening
- 21–60 years of age at time of screening

- Women of childbearing potential must agree to use at least one form of birth control (prescription hormonal contraceptives, diaphragm, IUD, condoms with or without spermicide, or voluntary abstinence) from time of study enrollment through study exit.
- Willing and able to provide informed consent

### **Key Exclusion Criteria**

- Previous bariatric, gastric pancreatic, hepatic, and/or splenic surgery
- History of duodenal or gastric ulcers or regularly taking medications (therapy >1 day per week) that can cause ulcers (e.g. aspirin, non-steroidal anti-inflammatory drugs)
- Prior radiation to the upper abdomen
- Prior embolization to the stomach, spleen or liver
- Portal venous hypertension
- Active H. pylori infection
- Uncontrolled hypertension (> 160/100 with or without medication).
- Diabetes (determined by medical history, fasting blood glucose or results of an oral glucose tolerance test)
- Serum triglyceride > 400 mg/dL at screening.
- Class 4 or 5 surgical risk based on standard ASA criteria (Saklad M. Grading of patients for surgical procedures. Anesthesiol. 1941; 2:281-4). Need to define these criteria here
- Severe pulmonary or cardiovascular disease defined as a history or evidence of serious cardiovascular disease, including myocardial infarction, acute coronary syndrome, coronary revascularization, heart failure requiring medications, history of sudden cardiac death, or NYHA (New York Heart Association) class III or IV heart failure (defined below):
  - Class III: patients with marked limitation of activity; they are comfortable only at rest.
  - Class IV: patients who should be at complete rest, confined to bed or chair; any physical activity brings on discomfort and symptoms occur at rest.
- Coagulation disorders (platelets < 100,000, PT > 2 seconds above control or INR > 1.5 at screening).
- Anemia (Hb  $\leq$  10.0 g/dL) at screening.
- Malignancy in the last 5 years (except for non-melanoma skin cancer).
- Evidence of other significant organ system dysfunction (e.g. cirrhosis, renal failure)
- Pregnant or lactating.
- History of substance abuse in last 3 years.
- Thyroid Stimulating Hormone (TSH) >2.0 x upper limit of normal at screening.
- Taking prescription or over-the-counter medications for weight loss in the last 3 months before screening, or planning to participate in a commercial weight loss program in the next 5 years.
- Taking diuretic medication for congestive heart failure or edema.
- Evidence of significant mucosal inflammation, ulceration or ischemia detected on endoscopy, and those with unsuitable left gastric anatomy as judged by the study site physician will be excluded.

- Psychiatric illness that could affect compliance with the study, as judged by the site principle investigator.
- Unable to complete screening requirements (compliance with visits and dietary record)
- Taking medication once or more per week that causes weight gain (e.g. atypical antipsychotics, monoamine oxidase inhibitors, lithium, selected anticonvulsants, tamoxifen, glucocorticoids)
- Chronic abdominal pain that would potentially complicate management.
- Unstable weight (>3% change; self-reported) over the previous 2 months at time of screening.
- Subjects whom the site investigator, research team, or the study medical monitor feel is not able to participate in the study for any reason, including poor general health or unable/unwilling to follow the study protocol.

**Follow-up Schedule**

- Screening
- Baseline visit
- Interventional Radiology Procedure
- Randomization
- Left Gastric Artery Occlusion / Placebo
- Follow-up Visits Week: 1, 2, 3, 4, 6, 8, 10, 12, 14, 16, 20, 24, 26, 28, 32, 36, 40, 44, 52
